6.5.3.2. Analysis

The UHDRS-TMS, UHDRS-TMC (physician rated) and UHDRS-TMD (physician rated) change from baseline to week 15 data will be analyzed using MMRM similarly to the description in Section [6.5.1.2](#).

6.5.4. Pediatric Evaluation of Disability Inventory Computer Adaptive Test Definition

The PEDI-CAT is a clinical assessment for children and youth. The PEDI-CAT (activities of daily living [ADL], parent/caregiver completed, content balanced version) measures function in 4 domains: (1) Daily Activities; (2) Mobility; (3) Social/Cognitive, and (4) Responsibility. Each domain is self-contained and can be used separately or with other domains. The content balanced version presents a balance of items from each of the Daily Activities domain's content areas (Getting Dressed, Keeping Clean, Home Tasks, and Eating & Mealtime). A total of approximately 30 items are administered (total number of items administered is dependent upon the responses and decision tree path). The PEDI-CAT software utilizes Item Response Theory statistical models to estimate a child's abilities from a minimal number of the most relevant items or from a set number of items within each domain. All respondents begin with the same item in each domain in the middle of the range of difficulty or responsibility and the response to that item then dictates which item will appear next (a harder or easier item), thus tailoring the items to the child and avoiding irrelevant items. The CAT program then displays the results: normative standard scores, scaled scores and the SE. The scales are available for 21 age groups as intervals of 1 year.

Normative (fit) scores are based on a child's chronological age and intended for use by clinicians so that they may interpret a particular child's functioning relative to others of the same age. This metric is of less relevance for the studied population and therefore will not be assessed.

Scaled scores provide a way to look at a child's current functional skills and progress in these skills over time. Scaled scores are especially helpful in documenting improvements in functional skills for children not expected to exhibit or regain normative levels of functioning. The scaled scores are based on an estimate of the placement of an individual child along the hierarchical scale within each domain. The PEDI-CAT scaled scores are currently on a 20 to 80 scale metric. See [PEDI-CAT \(Version 1.3.6\) Development, Standardization and Administration Manual](#).

The SE scores indicate the level of the test precision, and are expected to be up to 0.5.

The PEDI-CAT (ADL, parent/caregiver completed, content balanced version) is administered at baseline and at week 15/ET visits.

6.5.4.1. PED-CAT Analysis

The PEDI-CAT scaled score change from baseline to week 15 data will be analyzed using an ANCOVA model with age group at baseline, region, baseline score, and treatment as fixed effects based on the mITT analysis set. The ANCOVA model will be applied as in Section [6.2.4.2.1](#).

A descriptive summary of the PEDI-CAT scaled score will be provided for all measurements and change from baseline.

6.5.5. The CP module of the PedsQL (QoL, patient/caregiver)

6.5.5.1. Definition

The Pediatric Quality of Life Inventory (PedsQL™) is a health-related quality-of-life instrument that consists of a well-validated generic core measure and some condition and disease-specific modules (Varni et al 2006). The 35-item PedsQL 3.0 CP module encompasses 7 scales: (1) Daily Activities (9 items); (2) School Activities (4 items); (3) Movement and Balance (5 items); (4) Pain and Hurt (4 items); (5) Fatigue (4 items); (6) Eating Activities (5 items); and (7) Speech and Communication (4 items).

The scales comprise parallel child self-report and parent proxy-report formats. Child self-report includes ages 5 to 7 years, 8 to 12 years, and 13 to 18 years. A parent proxy report is included in reports for ages 2 to 4 years (toddler), 5 to 7 years (young child), 8 to 12 years (child), and 13 to 18 years (adolescent, not administered in the study), and assesses parents' perceptions of their child's health-related quality of life (QoL). The instructions ask how much of a problem each item has been during the past 1 month. A 5-point response scale is utilized across child self-report and parent proxy report as follows:

0=never a problem;

1=almost never a problem;

2=sometimes a problem;

3=often a problem;

4=almost always a problem.

To further increase the ease of use for the young child self-report (ages 5–7 years), the response scale is reworded and simplified to a 3-point scale (0=not at all a problem; 2=sometimes a problem; 4=a lot of a problem).

Items are reverse scored and linearly transformed to a 0–100 scale (0=100, 1=75, 2=50, 3=25, 4=0), so that higher scores indicate better quality of life, i.e. fewer symptoms or problems. Scale Scores are computed as the sum of the items divided by the number of items answered (this accounts for missing data). If more than 50% of the items in the scale are missing, the Scale Score is not computed. This computation is consistent with the previous PedsQL peer-reviewed publications as well as other well-established Health-related quality of life measures.

A total score will be computed as the sum of the 35 items divided by the number of items answered and will not be computed if more than 50% of the items are missing. Each teen/child self-report and parent proxy-report will be assessed separately.

The PedsQL is administered at baseline and at week 15/ET visits.

6.5.5.2. Analysis

The PedsQL total score per each teen/child self-report /parent proxy-report and change from baseline to week 15 will be analyzed using an ANCOVA model with region, baseline score, and

treatment as fixed effects based on the mITT analysis set. The ANCOVA model will be applied as in Section 6.2.4.2.1.

A descriptive summary of each PedsQL teen/child self-report /parent proxy-report total and scale scores and change from baseline will be provided.

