2.2. Randomization and Blinding

This is a double-blind study. Patients will be randomized to either TEV 50717 or matching placebo in a 2:1 ratio using Randomization and Trial Supply Management (RTSM). Patients will be stratified by age at baseline (6 to <12 years; 12 through 18 years, inclusive) and region (US; non-US). Patients and investigators will remain blinded to treatment assignment during the study. In addition, the sponsor’s clinical personnel and all vendors (with the exception of the RTSM vendor) will be blinded to the IMP identity until the database has been locked for analysis and the treatment assignments are revealed.

Patients re-entering the study will be manually assigned to their initial treatment group by the RTSM unblinded vendor. Blinding will be maintained for the patient, investigator, and sponsor as described above; the only information that will be available is that the patient was assigned to the same treatment group as previously.

The iDMC will perform an unblinded non-binding IA for futility and will monitor safety throughout the study based on unblinded data. An iDMC charter will be developed for the IA, and the procedures to ensure the integrity of the study will be provided in the charter.

In the event of an emergency, it will be possible to determine to which treatment group and dose the patient has been allocated by accessing the RTSM system. All investigational centers will be provided with details of how to access the system for code breaking at the start of the study. The medical monitor or equivalent should be notified following unblinding. Any unblinding of the IMP performed by the investigator must be recorded in the source documents.

The randomization list will be assigned to the relevant treatment groups through a qualified service provider (eg, via an RTSM system). The generation of the randomization list and management of the RTSM system will be done by a qualified service provider under the oversight of the responsible function at Teva.

Patient randomization codes will be maintained in a secure location at the service provider contracted to generate the codes.

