4.3.5.2. Other Missing Items in Rating Scales

Rules for handling missing items in efficacy and safety rating scales are presented in Section 6.4 (Unified Huntington’s Disease Rating Scale-Total Motor Score (UHDRS-TMS), Unified Huntington’s Disease Rating Scale-Total Maximal Chorea (UHDRS-TMC), Unified Huntington’s Disease Rating Scale-Total Maximal Dystonia (UHDRS-TMD), Pediatric Evaluation Disability Inventory-Computer Adapted Test (PEDI-CAT), Pediatric Quality of Life Inventory (PedsQL) and Patient Global Impression of Improvement (PGI-I)) and Section 8 (Columbia-Suicide Severity Rating Scale [C-SSRS], Child Behavior Checklist [CBCL], Extrapyrimal Symptom Rating Scale [ESRS] and Epworth Sleepiness Scale [ESS]).

Unless otherwise specified, only those observed data from the patients will be used in the statistical analyses, ie, no estimation of missing data.

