6.2.4.2.1. Analysis of Covariance

The ANCOVA model will be used for week 15 MD-CRS part II total score change from baseline data following imputation using the same approach as described in Section 6.2.3, steps 1-2. The ANCOVA model will replace the MMRM analysis in step 3 of Section 6.2.3 and will include age group at baseline, region, baseline MD-CRS part II total score, and treatment as covariates. The SAS code for this model is as follows:

```
proc mixed;  
  class arm agegrp region;  
  model chg=arm agegrp region base;  
  lsmeans arm / diff cl;  
where avisitn=15;  
run;
```

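### The PedsQL ANCOVA omits age group, yet the model it cites includes it; the same citation brings in an imputation that neither PedsQL nor PEDI-CAT can support

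*SAP*

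**What the plan says.** - **PedsQL model (SAP 6.5.5.2).** Each report's total score and its "change from baseline to week 15 will be analyzed using an ANCOVA model with region, baseline score, and" treatment. Age group is not listed. The paragraph continues: "The ANCOVA model will be applied as in Section 6.2.4.2.1".
- **The cited model (SAP 6.2.4.2.1).** It "will include age group at baseline, region, baseline MD-CRS part II total score, and treatment as covariates", and its SAS code carries the age-group term. It is fitted after the imputation of Section 6.2.3, steps 1–2.
- **PEDI-CAT (SAP 6.5.4.1).** The same citation, but the list is "age group at baseline, region, baseline score, and treatment as fixed effects".
- **Randomisation (SAP 2.2).** "Patients will be stratified by age at baseline" (6 to <12; 12 through 18) and by region.
- **Unit of analysis for PedsQL.** 6.5.5.2 refers to "The PedsQL total score per each teen/child self-report /parent proxy-report". 6.5.5.1 says "Each teen/child self-report and parent proxy-report will be assessed separately" and defines the forms by age band: 5–7, 8–12 and 13–18 years.
- **Missing data.** 4.3.5.2 names both scales and says that, unless otherwise specified, "only those observed data from the patients will be used in the statistical analyses".

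**The concern.** There are two defects, both arising from the citation of Section 6.2.4.2.1.

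**Covariates.** The local list and the cited model disagree on age group, and nothing says which governs. Age group appears in the primary MMRM, the Global Index model, PEDI-CAT, PGI-I and the stratified responder test. The other model without it is the sensitivity analysis that is explicitly described as having fewer covariates (6.2.4.2.2). If a stratification factor is prognostic and is left out, the residual variance absorbs it. The treatment estimate is still protected by the stratified allocation, but the reported standard error is too large: intervals are too wide and the test is conservative.

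**Imputation.** The cited section is an ANCOVA on imputed data. Taken literally, the citation carries over an imputation model that uses week 9 and week 12 scores. PedsQL and PEDI-CAT have no such scores.

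At stake is which model is fitted, and to which data. The plan should settle both before unblinding.

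**Working it through.** **Plan's own figure.** The SAP states no standard error, power or sample size for PedsQL, so there is none to reproduce on this point.

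**Step 1: the two models side by side.**

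| Source | Treatment | Region | Baseline score | Age group |
|---|---|---|---|---|
| 6.5.5.2, PedsQL list | yes | yes | yes | **no** |
| 6.2.4.2.1, cited text and code | yes | yes | yes (MD-CRS part II) | **yes** |
| 6.5.4.1, PEDI-CAT list | yes | yes | yes | **yes** |

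**Step 2: where age group can matter.** The strata split at 12 years, and enrolled ages are 6 to 18.

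| PedsQL form | Enrolled ages below 12 | Enrolled ages 12 and over |
|---|---|---|
| 5–7 | 6, 7 | none |
| 8–12 | 8–11 | 12 |
| 13–18 | none | 13–18 |

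If each form is analysed alone, age group is constant in the first and third. It cannot be estimated there, and omitting it changes nothing. In the 8–12 form it can be estimated, but only 12-year-olds are in the upper stratum. Section 6.5.5.1 also appears to say that the 13–18 parent proxy is not administered. Even pooled proxy reports would then cover ages 6–12 only. A pooled self-report analysis would span both strata fully.

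**Step 3: size when both strata are present.** Let R² be the share of outcome variance, after the other terms, that age group explains. The SAP gives no value, so a range is assumed. With allocation balanced within strata,

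SE(age omitted) / SE(age included) ≈ 1/√(1 − R²).

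| Assumed R² | Formula | Simulated, 65 patients, 2:1 within two equal age strata |
|---|---|---|
| 0 | 1.00 | 1.00 |
| 0.02 | 1.01 | 1.01 |
| 0.05 | 1.03 | 1.03 |
| 0.06 | 1/√0.94 = 1.03 | 1.03 |
| 0.10 | 1.05 | 1.06 |
| 0.14 | 1/√0.86 = 1.08 | 1.08 |
| 0.15 | 1.08 | 1.09 |
| 0.20 | 1/√0.80 = 1.12 | 1.12 |

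For an 8–12 form with an assumed 22 patients, 20% of them aged 12, the simulated ratio is 0.997 at R² = 0 and 1.03 at R² = 0.05.

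**Step 4: effect on the test.** Omitting age from 65 patients leaves 65 − 4 = 61 degrees of freedom and a critical value of 2.00. At R² = 0.20 the effective critical value is 2.00 × 1.118 = 2.24. The nominal two-sided 5% test then rejects in about 2.9% of null trials (half that one-sided). Separate simulations gave 2.7% and 3.2%. At R² = 0.05 the same calculation gives about 4.5%. The error is on the conservative side throughout.

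**Step 5: the imputation.**
- 6.2.4.2.1 requires Section 6.2.3, steps 1–2, whose imputation models use scores at weeks 9 and 12.
- Sections 6.5.4 and 6.5.5.1 schedule PEDI-CAT and PedsQL at baseline and week 15/early termination only. The imputation cannot be run as written on their own scores.
- 6.2.4.3 cites the same ANCOVA and expressly excludes the multiple imputation. 6.5.4.1 and 6.5.5.2 cite it without that exclusion.
- 4.3.5.2 makes observed data the default unless otherwise specified. An unqualified citation of an imputed-data ANCOVA could be read as specifying otherwise.

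**The case against.** **The standard error is too large, full stop.** A reader might infer this from the omission of a stratum. The documents do not support it without conditions. It requires age to predict PedsQL change after baseline adjustment, and the SAP gives no such figure. That forms and response options differ by age concerns the level of the score. The outcome is change, with baseline already in the model. Under analysis by form, two of the three bands lie within a single stratum. This part of the objection stands and limits the point.

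**The omission may be deliberate.** PedsQL is split by age-banded form and PEDI-CAT is not, so different covariates could follow from that. The difference from PEDI-CAT is therefore not an error in itself. But the SAP does not give this reason, and the code it cites would still contain a term that cannot be estimated in two bands. The contradiction remains under either reading.

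**The general rules already exclude imputation.** Section 4.3 places multiple imputation in the primary and secondary analyses, and 4.3.5.2 defaults to observed data. Also, Table 2 assigns an early-termination PedsQL or PEDI-CAT value from day 2 to end of treatment to week 15, so fewer values would be missing. This makes the observed-data reading the more natural one and the practical effect smaller. It does not remove the ambiguity, because 6.2.4.3 shows that the plan excludes imputation expressly when it cites the same ANCOVA.

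**Pooling.** A reader might conclude that all self-reports, or all proxy reports, should be pooled so that age can be adjusted for. That is a separate analysis choice, it may conflict with the separate assessment in 6.5.5.1, and it does not follow from this point.

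**Conclusion.** The point holds as an internal contradiction with a limited, conditional consequence. Section 6.5.5.2 supports two covariate sets. In any PedsQL analysis spanning both age strata, leaving out age group inflates the model standard error by about 3% at an assumed 5–6% of variance explained, 12% at 20%, and 0% if age is not prognostic. In a form confined to ages 6–7 or 13–18 the effect is exactly zero. These sizes rest on assumed variance shares and, for the simulated pooled case, on 65 patients allocated 2:1 within two equal age strata. Any error is a loss of precision, not a false-positive risk.

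Separately, the citation in 6.5.4.1 and 6.5.5.2 brings in an imputation that cannot be run as described for either scale and that conflicts with the observed-data default.

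PedsQL and PEDI-CAT are other efficacy endpoints outside the multiplicity control of Section 7. Primary and key secondary conclusions are not touched.

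**What to change.** 1. **Section 6.5.5.2:** add age group at baseline to every PedsQL ANCOVA whose patients span both age strata. State that the term is dropped from the code only where it is constant.
2. **Sections 6.5.4.1 and 6.5.5.2:** qualify the citation, for example *as in Section 6.2.4.2.1 but without the multiple imputation*, in line with 6.2.4.3 and 4.3.5.2.

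No pooling of self-report or proxy forms is required. The cost is a change of SAP wording and at most 1 degree of freedom. With 65 patients that moves the critical value only from 1.9996 (61 df) to 2.0003 (60 df). In a form as small as the assumed 22 patients, with age not prognostic at all, the simulated interval is under 1% wider.

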6.5.6. PGI-I Scale (global, patient/caregiver)

6.5.6.1. Definition

For a detailed description of scales, refer to the Section 6.3.7 of the study protocol.

The PGI-I is administered at week 3, week 7, week 9, week 12, week 15/ET, and week 16/EOS visits. Input from the caregiver/adult is permitted.

6.5.6.2. Analysis

The PGI-I at week 15 data will be analyzed using MMRM based on the mITT analysis set similarly to the description in Section 6.5.1.2 (except that the value at week 15 will be analyzed rather than the change from baseline). The MMRM model will include age group at baseline, week (3 levels: weeks 9, 12, and 15), region, and treatment as fixed effects. No baseline assessment will be used in the model.

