4.4. Study Days and Visits

Study days will be numbered relative to the baseline visit date. Day 1 is defined as the date of the baseline visit, and the first dose of the IMP will be taken the next morning (day 2). Days will be numbered relative to baseline (ie, ..., -2, -1, 1, 2, ...; day -1 being the day before the baseline visit).

For efficacy and safety by-visit analyses, data collected at post-baseline scheduled visits will be included using their scheduled visit.

Data collected at early termination and unscheduled visits will be included and assigned to a visit window as described below.

Table 2: Visit Windows for Early Termination Visit for Efficacy Assessments

Assessment ^a	Study Day Window	Scheduled Day	Scheduled Visit/Week
MD-CRS	Day 2 - 73	Day 63	Week 9
	Day 74 - 94	Day 84	Week 12
	Day 95 - EOT	Day 105	Week 15
	≥Day after EOT	Day 112	Week 16
CaGI-I, CGI-S, PGI-I	Day 2 - 35	Day 21	Week 3
	Day 36 - 53	Day 49	Week 7
	Day 54 - 73	Day 63	Week 9
	Day 74 - 94	Day 84	Week 12
	Day 95 - EOT	Day 105	Week 15
	≥Day after EOT	Day 112	Week 16
CGI-I	Day 2 - 10	Day 7	Week 1
	Day 11 - 17	Day 14	Week 2
	Day 18 – 24	Day 21	Week 3
	Day 25 - 31	Day 28	Week 4
	Day 32 - 38	Day 35	Week 5
	Day 39 - 45	Day 42	Week 6
	Day 46 - 53	Day 49	Week 7
	Day 54 - 73	Day 63	Week 9
	Day 74 - 94	Day 84	Week 12
	Day 95 - EOT	Day 105	Week 15
	≥Day after EOT	Day 112	Week 16
PEDI-CAT, PedsQL	Day 2 – EOT	Day 105	Week 15

Assessment ^a	Study Day Window	Scheduled Day	Scheduled Visit/Week
UHDRS-TMS, UHDRS-TMC, UHDRS-TMD	Day 2 - 73	Day 63	Week 9
	Day 74 - 94	Day 84	Week 12
	≥Day 95 - EOT	Day 105	Week 15

^a CaGI-I=Caregiver Global Impression of Improvement; CGI-I=Clinical Global Impression of Improvement; CGI-S=Clinical Global Impression of Severity; PGI-I=Patient Global Impression of Improvement; UHDRS-TMS=Unified Huntington’s Disease Rating Scale-Total Motor Score; UHDRS-TMC=Unified Huntington’s Disease Rating Scale-Total Maximal Chorea; UHDRS-TMD=Unified Huntington’s Disease Rating Scale-Total Maximal Dystonia; EOT=end of treatment

Table 3: Visit Windows for Early Termination Visit for Safety Assessments

Assessment ^a	Study Day Window	Scheduled day	Scheduled Visit/Week
Vital signs, Weight, C-SSRS, ESRS, CBCL- Syndrome Scale, ESS	Day 2 - 35	Day 21	Week 3
	Day 36 - 53	Day 49	Week 7
	Day 54 - 74	Day 63	Week 9
	Day 75 - 94	Day 84	Week 12
	Day 95 – EOT	Day 105	Week 15
	≥Day after EOT	Day 112	Week 16
ECG	Day 2 - 35	Day 21	Week 3
	Day 36 - 67	Day 49	Week 7
	Day 68 – EOT	Day 105	Week 15

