6.3.1.1. Key Secondary Efficacy Endpoints Analysis

Analyses of the key secondary endpoints will be performed in a hierarchical manner as follows:

1. MD-CRS part I total score change from baseline to week 15 will be analyzed using a MMRM in the same fashion as the primary analysis, with the exception that the baseline value of MD-CRS part I total score will be included as the covariate instead of MD-CRS part II total score.

2. CaGI-I at week 15 will be analyzed using an MMRM model in the same fashion as the primary analysis, with the exceptions that the baseline value of CGI-S will be included as the covariate instead of MD-CRS part II total score and that the week variable will include 5 levels (weeks 3, 7, 9, 12, and 15).
3. CGI-I at week 15 will be analyzed using an MMRM model in the same fashion as the primary analysis, with the exceptions that the baseline value of CGI-S will be included as the covariate instead of MD-CRS part II total score and that the week variable will include 5 levels (weeks 3, 7, 9, 12, and 15).
4. UHDRS-TMC (centrally-read) change from baseline to week 15 will be analyzed using an MMRM model in the same fashion as the primary analysis, with the exception that the baseline value of UHDRS-TMC (centrally-read) will be included as the covariate instead of MD-CRS part II total score.
5. UHDRS-TMD (centrally-read) change from baseline to week 15 will be analyzed using an MMRM model in the same fashion as the primary analysis, with the exception that the baseline value of UHDRS-TMD (centrally-read) will be included as the covariate instead of MD-CRS part II total score.

For CaGI-I and CGI-I, in [Appendix 1](#), Step 1 should begin with week 3, week 7 and only then continue to week 9.

See Section [6.5.3](#) for definition of UHDRS-TMC and TMD, and Section [7](#) for description of multiplicity control of the key secondary endpoints.

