6.5.7. CGI-S Scale (global, physician rated)

6.5.7.1. Definition

For a detailed description of the scale, refer to the Section 6.3.8 of the study protocol.

The CGI-S is administered at screening, baseline, week 3, week 7, week 9, week 12, week 15/ET, and week 16/EOS visits.

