7. MULTIPLE COMPARISONS AND MULTIPLICITY

The primary efficacy endpoint will be tested at the 1-sided significance level of $\alpha=0.025$.

If the primary endpoint is statistically significant (p-value ≤ 0.025), the 5 key secondary hypotheses will be tested using a hierarchical approach at the 1-sided significance level of $\alpha=0.025$, in the following order: (1) MD-CRS part I total score, (2) CaGI-I, (3) CGI-I, (4) UHDRS-TMC (centrally-read), and (5) UHDRS-TMD (centrally-read)

No multiplicity control will be applied to the sensitivity analysis or other endpoints.

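### The PGI-I model leaves out baseline CGI-S and the collected week 3 and week 7 ratings, so some early leavers in the mITT set contribute nothing to it

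*SAP*

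**What the plan says.** **PGI-I.** Section 6.5.6.1 gives the schedule: "The PGI-I is administered at week 3, week 7, week 9, week 12, week 15/ET, and week 16/EOS visits". Section 6.5.6.2 then specifies: "The MMRM model will include age group at baseline, week (3 levels: weeks 9, 12, and 15), region, and treatment as fixed effects". It adds "No baseline assessment will be used in the model", names the mITT set, and points to the Section 6.5.1.2 template.

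**CaGI-I and CGI-I.** These are also improvement ratings without a baseline value of their own. On visits, Section 6.3.1.1 says of each: "the week variable will include 5 levels (weeks 3, 7, 9, 12, and 15"). On adjustment, the same section says of each: "the baseline value of CGI-S will be included as the covariate instead of MD-CRS part II total score".

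**Baseline severity.** Section 6.5.7.1 confirms that it is available: "The CGI-S is administered at screening, baseline, week 3, week 7, week 9, week 12, week 15/ET, and week 16/EOS visits".

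**Visit windows.** Section 4.4, Table 2 puts "CaGI-I, CGI-S, PGI-I" in one group for early-termination ratings: days 2–35 go to week 3, days 36–53 to week 7, and days 54–73 to week 9. For MD-CRS, the whole span of days 2–73 goes to week 9.

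**Status.** PGI-I is listed among the other efficacy endpoints in Section 6.5. Section 7 says "No multiplicity control will be applied to the sensitivity analysis or other endpoints", and the template in Section 6.5.1.2 labels its p-value nominal.

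**The concern.** Three global improvement scales are collected in the same trial. Two are adjusted for baseline CGI-S and modelled from week 3. The third is not, and the SAP gives no reason.

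Two things follow. First, a repeated-measures model uses incomplete patients under a missing-at-random assumption only through visits that are in the model. Taking out weeks 3 and 7 removes exactly the ratings that patients who leave during titration have. Second, a baseline severity measure already in the database is not used to reduce residual variance in a trial of about 65 patients.

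What is at stake is precision and the use of early leavers' data for one supportive endpoint. Type I error and the primary conclusion are not affected.

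**Working it through.** The SAP states no power, variance or dropout figure for PGI-I, so there is none to reproduce. The check compares sections and adds two small illustrations.

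**1. Which patients fall out of the PGI-I model**

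Inputs: the mITT definition in Section 3.2 (at least one post-baseline centrally read MD-CRS part II), Table 2 in Section 4.4, and the model weeks in Section 6.5.6.2. Section 4.3.5.2 adds that only observed data are used unless otherwise specified, and Section 6.5.6.2 specifies no imputation.

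| Patient | MD-CRS part II | In mITT? | PGI-I mapped to | In PGI-I model (weeks 9, 12, 15)? |
|---|---|---|---|---|
| Early-termination visit on day 50, MD-CRS centrally read | week 9 | yes | week 7 | no |
| Early-termination visit on day 30, MD-CRS centrally read | week 9 | yes | week 3 | no |
| Early-termination visit on day 58, MD-CRS centrally read | week 9 | yes | week 9 | yes |
| Leaves by day 53 with no post-baseline central MD-CRS | none | no | week 3 or 7, if rated | no, and outside the set anyway |

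The first two rows are the affected group. They count in the primary analysis and have observed PGI-I ratings, yet contribute nothing to the PGI-I estimate. The day-50 patient's CaGI-I and CGI-I ratings both map to week 7 and are in those models.

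**2. How many patients this could be**

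The SAP gives no dropout rate by day 53. Assume 5–10% of about 65 patients (Section 2.4):

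- 65 × 0.05 = 3.25
- 65 × 0.10 = 6.5

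That is about 3 to 6 patients. It is a ceiling under this assumption, because only those in mITT with an observed week 3 or week 7 PGI-I count.

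**3. Precision from baseline CGI-S**

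Let r be the correlation between baseline CGI-S and week 15 PGI-I (assumed). Residual variance is multiplied by 1 − r², and the standard error by √(1 − r²).

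| r | Variance ratio | SE ratio |
|---|---|---|
| 0.1 | 1 − 0.01 = 0.99 | 0.995 |
| 0.2 | 1 − 0.04 = 0.96 | 0.980 |
| 0.3 | 1 − 0.09 = 0.91 | 0.954 |
| 0.4 | 1 − 0.16 = 0.84 | 0.917 |

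**4. Cost in covariance parameters**

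An unstructured matrix for k visits has k(k + 1)/2 parameters: 3 × 4/2 = 6 now and 5 × 6/2 = 15 with weeks 3 and 7 added.

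**The case against.** The strongest reply is that nothing here is wrong or contradictory. PGI-I has no baseline rating, so the sentence excluding one is correct as written, and randomization keeps the comparison valid without a covariate. The SAP is also consistent by tier. The five-week models belong to the hierarchically tested key secondary endpoints, while the other endpoints follow the three-week template. CGI-S itself follows that template (Section 6.5.7.2) although it too is rated at weeks 3 and 7. Early PGI-I data do appear elsewhere: Section 6.5.8 reports responders at each visit, with a sensitivity analysis that counts missing patients as non-responders over the whole mITT set.

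The precision gain is uncertain as well. One more coefficient with about 65 patients costs roughly 1/60, or 1.7%, in variance. At r = 0.1 the net is 0.99 × 1.017 ≈ 1.007, which is no gain.

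All of this stands and keeps the point small. It does not explain why ratings already collected are left out, or why a covariate and visit structure accepted for two similar scales is not used for the third.

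A reader might infer more than the SAP supports:

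- **That everyone who leaves before week 9 is lost.** Table 2 maps PGI-I early-termination ratings on days 54–73 to week 9, so those patients are already in the model.
- **That adding weeks 3 and 7 recovers every early leaver.** Patients without a post-baseline central MD-CRS stay outside mITT. The others inform week 15 only through the estimated covariance, under MAR.
- **That the three scales would then be analysed alike.** CaGI-I and CGI-I also use the MAR/MNAR multiple imputation of Section 6.2.3, and the PGI-I categories shown in Section 6.6.1 differ in number and label.

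**Conclusion.** The point holds as a low-severity, cheap improvement. The PGI-I MMRM leaves out baseline CGI-S and two collected visits that the CaGI-I and CGI-I models use. The concrete result is that mITT patients who terminate by day 53, with an early-termination MD-CRS mapped to week 9, are absent from the PGI-I analysis.

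The size rests on two assumptions that the SAP does not supply: the share of patients leaving by day 53, and the correlation r. Over the ranges shown, at most a few patients are affected, and the precision gain runs from about nil to 16% of residual variance before the small cost of the extra coefficient. The treatment comparison remains valid, and no confirmatory claim depends on it.

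**What to change.** In Section 6.5.6.2, fit the PGI-I MMRM with treatment, week (3, 7, 9, 12, 15), treatment by week, age group, region and baseline CGI-S. Naming the interaction also removes a small ambiguity: the current list of effects omits it, while the template code in Section 6.5.1.2 includes it.

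Also:

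- apply the covariance fallback order of Section 6.2.3 if the unstructured model does not converge;
- extend the baseline CGI-S rule of Section 4.3.3, now limited to the CGI-I analysis, to PGI-I.

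If the sponsor prefers the present model, one sentence giving the reason would do.

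The cost is a few sentences and no new data. The downside is 15 instead of 6 unstructured covariance parameters, which the SAP already accepts for CaGI-I and CGI-I. The change makes the fixed effects of the three global scales alike, but not the full analyses, because PGI-I would still not be multiply imputed.
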